4.8.8 Drug levels

The study investigates two questions regarding the potential interactions between antimalarial drugs and vaccines.

- 1) Does the co-administration of antimalarial drugs with vaccines influence vaccine antibody levels
- 2) Does the co-administration of antimalarial drugs with vaccines influence drug levels

The second question will be addressed for piperazine and primaquine. Piperazine levels will be assessed during each round (M0, M1, and M2) on Day 0, 1, 2, and 7 (M0D0 drug level will be

assessed if additional data are required). Primaquine levels will be assessed during each round 24hrs after drug administration. Additional drug level assessment for Primaquine will be done if additional data are required.

The drug levels will be assessed in the 60 participants who receive vaccine and drugs (groups 4 and 6). The drug levels will be compared to historic controls.

4.9 Definition of Start and End of Trial

The start of the trial is defined as the date of the first vaccination of the first participant. The end of trial is the date of the last visit of the last participant, which would be a maximum of 6 months after recruitment and first vaccination of the last participant.

4.10 Participant withdrawal from the study

Each participant has the right to withdraw from the study at any time and for any reason, and is not obliged to give his or her reasons for doing so. Participants who are withdrawn because of AEs must be clearly distinguished from participants who are withdrawn for other reasons. For all withdrawals due to SAE/AEs, appropriate follow-up visits or medical care will be arranged, with the agreement of the participant, until the SAE/AE has resolved and stabilized

From an analysis perspective, a 'withdrawal' from the study is any participant who did not come back for the concluding visit or was not available for the concluding contact foreseen in the protocol. A participant qualifies as a 'withdrawal' from the study when no study procedure has occurred, no follow-up has been performed and no further information has been collected for this participant from the date of withdrawal/last contact. Investigators will make an attempt to contact those participants who do not return for scheduled visits or follow-up.

In addition participant may be withdrawn from the study by the investigator at any time, if it is in the best interests of the participant's health and well-being, or for any of the following reasons:

- Ineligibility (either arising during the study or retrospectively, having been overlooked at screening).
- Significant protocol deviation.
- Participant non-compliance with study requirements.
- An AE, which requires discontinuation of the study involvement or results in inability to continue to comply with study procedures.

If a participant withdraws from the study, blood samples collected before their withdrawal from the trial will be used/stored unless the participant specifically requests otherwise. Data collected prior to the withdrawal of a participant will be used.

In all cases of participant withdrawal or discontinuation, excepting those of complete consent withdrawal, long-term safety data collection will continue as appropriate if subjects have received one or more vaccine doses.

4.11 Participant withdrawal from the study agent

Participants withdrawn from the study agent are those who do not receive the complete number of vaccine doses. A participant withdrawn from the study agent may not necessarily be withdrawn from the study, as further procedures or follow-up may be performed (safety or immunogenicity) if planned in the study protocol. Information relative to premature discontinuation of the study agent will be documented in the CRF. The investigator will document whether the decision to discontinue further vaccination was made by the participant or the investigator and which of the following possible reasons was responsible for withdrawal:

- serious adverse event,
- non-serious adverse event,
- other (specify).

Subjects with positive microscopy result indicating malaria on vaccination days at Month 1 or Month 2 will be treated according to national guidelines and the volunteer will be withdrawn from further vaccination.

4.12 Pregnancy

Participants are informed that the safety of the vaccine in pregnancy is unknown. Female study participants are asked to use appropriate contraceptive methods to prevent pregnancy while they receive vaccinations. Appropriate contraceptive methods include:

- Established use of oral, injected or implanted hormonal contraceptives
- Intrauterine Device or Intrauterine System
- Barrier methods (condoms or diaphragm with additional spermicide)
- Male sterilisation (with appropriate post-vasectomy documentation of absence of sperm in the ejaculate)

- True abstinence, when this is in line with the preferred and usual lifestyle of the subject. Periodic abstinence (e.g., calendar, ovulation, symptothermal, post-ovulation methods) and withdrawal are not acceptable methods of contraception.

Female participants will be tested for pregnancy immediately prior to each vaccination.

Should a participant become pregnant during the trial, she will be followed up as other volunteers and in addition will be followed until pregnancy outcome, with the participant's permission. We will not routinely perform venepuncture on such participants.

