4.2 Primary Outcome Measures

The primary outcome measures will be:

- The safety of the investigational vaccine in each group:
 - Occurrence of serious adverse events (SAEs) from the date of the first vaccination to 29 days after the last vaccination, according to the MedRA classification.
 - Occurrence of SAEs during the whole study period, i.e. during a 6 month follow up period from the receipt of first vaccination, according to the MedRA classification.

- For groups 1 to 6, the concentration of antibodies against *Plasmodium falciparum* circumsporozoite (anti-CS antibody), one month after the first dose (at Study month 1), one month after the second dose (at Study month 2), one month after the third dose (at Study Month 3) and six months after the first dose (at Study Month 6).
- For group 7, the concentration of antibodies against *Plasmodium falciparum* circumsporozoite (anti-CS antibody), one month after the first dose (at Study month 1), two months after the first dose (at Study month 2), one month after the second dose (at Study month 3), and six months after the first dose (at Study Month 6).

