4.3.3 Exclusion Criteria

The following criteria should be checked at the time of study entry. If ANY exclusion criterion applies, the subject must not be included in the study:

- Female participant who is pregnant, lactating or planning pregnancy during the course of the study.
- Presence of any condition which in the judgment of the investigator would place the participant at undue risk or interfere with the results of the study (e.g. serious underlying cardiac, renal, hepatic or neurological disease; severe malnutrition; congenital defects or febrile condition).
- Hepatitis B surface antigen (HBsAg) detected in serum.
- Screening ECG demonstrates a QTc interval ≥ 450 ms

- Seropositive for hepatitis C virus (antibodies to HCV) at screening (unless has taken part in a prior hepatitis C vaccine study with confirmed negative HCV antibodies prior to participation in that study, and negative HCV RNA PCR at screening for this study).
- Anaemia (Hb < 10 g/dL)
- Positive malaria parasitaemia at screening or baseline (Month 0, Day 0).
- Use of any investigational or non-registered product or investigational use of a registered product (drug or vaccine), other than the study vaccines, during the period from the date of screening to the first vaccination, or planned use during the study period.
- Any medical condition that in the judgment of the investigator would make intramuscular (IM) injection unsafe.
- Any medical condition that in the judgment of the investigator would make the administration of the antimalarial treatment unsafe, such as prior allergic reactions to one or more component of the drug regimen: artemisinin, piperazine or primaquine.
- Contraindications to the use of artemisinin, piperazine or primaquine or use of medications known to have a potentially clinically significant interaction with these medications.
- Chronic administration (defined as more than 14 days in total) of immunosuppressants or other immune-modifying drugs during the period starting six months prior to the first vaccine dose. For corticosteroids, this will mean prednisone > 20 mg/day (for adult subjects), or equivalent. Inhaled and topical steroids are allowed.
- Planned administration/administration of a vaccine not foreseen by the study protocol in the period starting seven days before the first dose.

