5.1.2 Anti-malarial therapy

Participants in Groups 4 and 6 will receive three rounds of antimalarial drugs - each round starting on the day of vaccination (Day 0) at Study Months 0, 1 and 2. Participants in Group 7 will receive two rounds of antimalarial drugs – each round starting on the day of vaccination (Day 0) at Study months 0 and 2. Each round consists of three daily doses of co-formulated dihydroartemisinin/piperaquine on Day 0, 1, and 2 (i.e. the day of vaccination and each day for 2 days after). Dihydroartemisinin/piperaquine tablets (Guilin Pharmaceutical Company or Sigma Tau Pharmaceuticals) for adult patients each contain 40mg dihydroartemisinin and 320mg piperaquine with a therapeutic dose range between 2–10 mg/kg/day dihydroartemisinin and 16–26 mg/kg/dose piperaquine. In addition each participant will receive a single low dose primaquine on the day of vaccination (Day 0). One single low dose primaquine of approximately 0.25mg/kg (Thai Government Pharmaceutical Organisation) will be administered. This drug regimen has been used in mass drug administrations in more than 10,000 participants which have established that this antimalarial drug regimen is safe and effective.

In the unexpected event that volunteers are found to be infected with malaria during screening, baseline or during follow-up examination they will be treated according to the most up-to-date government guidelines.

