6.12 Events or outcomes not qualifying as adverse events or serious adverse events

6.13 Pregnancy

Female volunteers who are pregnant or intend to become pregnant will not be enrolled. Female subjects who become unexpectedly pregnant during of vaccination period (M0 to M2) must not receive additional doses of study vaccines but may continue other study procedures at the discretion of the investigator. While pregnancy itself is not considered an AE or SAE, any adverse pregnancy outcome or complication or elective termination of a pregnancy for medical reasons will be recorded and reported as an AE or a SAE.

The following should always be considered as SAE

- Spontaneous pregnancy loss, including:
 - spontaneous abortion, (spontaneous pregnancy loss before/at 22 weeks of gestation)
 - ectopic and molar pregnancy

- stillbirth (intrauterine death of foetus after 22 weeks of gestation).
- Any early neonatal death (i.e. death of a live born infant occurring within the first 7 days of life).
- Any congenital anomaly or birth defect identified in the offspring of a study subject (either during pregnancy, at birth or later) regardless of whether the foetus is delivered dead or alive. This includes anomalies identified by prenatal ultrasound, amniocentesis or examination of the products of conception after elective or spontaneous abortion.

Furthermore, any SAE occurring as a result of a post-study pregnancy AND considered by the investigator to be reasonably related to the investigational vaccines will be reported. While the investigator is not obligated to actively seek this information from former study participants, he/she may learn of a pregnancy through spontaneous reporting.

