6.21 Safety (ANALYSIS)

- Safety and reactogenicity of the investigational vaccine for each vaccination schedule:
 - Occurrence of solicited local and general AEs within seven days (day of vaccination and six subsequent days) after each vaccination.
 - Occurrence of unsolicited AEs from the date of the first vaccination to 29 days after the last vaccination, according to the Medical Dictionary for Regulatory Activities (MedDRA) classification.
 - Occurrence of SAEs (all, fatal, related to investigational vaccine) within 30 days (day of vaccination and 29 subsequent days) after each vaccination, according to the MedDRA classification.
 - Occurrence of SAEs (all, fatal, related to investigational vaccine) during the whole study period according to the MedDRA classification.
 - Occurrence of AEs and SAEs leading to withdrawal from further vaccination from Dose 1 (Day 0) up to study conclusion (Day 180), according to the MedDRA classification, for each vaccinated subjects.
 - Occurrence of pIMDs from Dose 1 (Day 0) up to study conclusion (Day 180), according to the MedDRA classification, for each vaccinated subjects.
 - Occurrence of meningitis from Dose 1 (Day 0) up to study conclusion (Day 180), according to the MedDRA classification, for each vaccinated subjects.

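### Section 4.12 ends the contraception request with the vaccination course and sets no interval after the last dose, although it calls vaccine safety in pregnancy unknown

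*Protocol*

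**What the plan says.** Section 4.12 opens with "Participants are informed that the safety of the vaccine in pregnancy is unknown". The next sentence sets the only contraception rule in the protocol: "Female study participants are asked to use appropriate contraceptive methods to prevent pregnancy while they receive vaccinations". A list of acceptable methods follows, with no end date other than that phrase. The same section requires a pregnancy test before each vaccination, follows any pregnancy during the trial to its outcome, and says that pregnant participants will not routinely be bled.

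Three other places bear on the point:

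- Section 4.3.3 excludes any "Female participant who is pregnant, lactating or planning pregnancy during the course of the study".
- Section 6.13 stops further doses for a woman who becomes pregnant in the "vaccination period (M0 to M2) must not receive additional doses of study vaccines".
- Sections 4.2 and 6.21 continue adverse-event follow-up beyond the last dose. Section 4.2 has as a primary outcome "Occurrence of serious adverse events (SAEs) from the date of the first vaccination to 29 days after the last vaccination", and 6.21 uses the same 29-day limit for unsolicited events.

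**The concern.** The two opening sentences of 4.12 pull in different directions. If safety in pregnancy is unknown, the precaution should outlast the final exposure by some interval. As written it stops when vaccination stops. A woman who meets the entry criteria and complies fully is not asked to avoid pregnancy in the days and weeks just after her last dose.

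What is at stake is mainly participant protection: an unplanned pregnancy, or a change of plan, soon after the last vaccine dose and, in Groups 4, 6 and 7, soon after the last antimalarial doses. There is a secondary effect on data. Because pregnant women are not routinely bled, a pregnancy in that period could cost a Month 3 or Month 6 anti-CS sample. Those samples are primary outcomes, in groups of 20 or 30 where section 8.2 stresses keeping losses low. The protocol gives no number of women and no expected pregnancy rate, so no numerical effect can be claimed.

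**Working it through.** There is no planned figure to reproduce. The check sets the sections side by side and adds date arithmetic from the visit-interval table in Appendix A.

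**1. Does any section extend the request?** Section 4.3.3 screens intent at entry. Section 4.5 makes pregnancy a bar to further doses. Section 6.13 covers stopping doses and reporting outcomes. Appendix A schedules urine pregnancy tests at screening and on Day 0 of Months 0, 1 and 2. None of these sets a contraception period after the last dose, and no test is scheduled after Month 2 Day 0.

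**2. When is the last dose?** Month 0 to Month 1 and Month 1 to Month 2 are each 28 days, ±7. The last vaccination is therefore nominally on study Day 28 + 28 = 56 (range 21 + 21 = 42 to 35 + 35 = 70).

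**3. How long after that dose does the protocol look for harm?**

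| Item | Days after last vaccination |
|---|---|
| Contraception request (4.12) | 0 |
| Unsolicited AEs (6.21); first SAE window (4.2) | 29 |
| Month 6 visit (Appendix A) | 28 + 84 = 112 (21 + 70 = 91 to 35 + 98 = 133) |
| pIMDs and meningitis, to Day 180 (6.21) | 180 − 56 = 124 (180 − 70 = 110 to 180 − 42 = 138) |

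**4. Antimalarial doses.** Under 5.1.2, "Each round consists of three daily doses of co-formulated dihydroartemisinin/piperaquine on Day 0, 1, and 2". In Groups 4, 6 and 7 the last dose is therefore taken two days after the last vaccination. A 29-day rule runs 29 − 2 = 27 days beyond it. The protocol itself expects drug to be measurable later than Day 2: section 4.8.7 schedules piperaquine levels in Groups 4 and 6 at Day 7 of each round, and at Day 0 of Months 1 and 2.

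**5. Should the rule end at a fixed visit such as Month 3?** Month 3 is 28 days after the Month 2 dose, but sections 4.5 and 4.11 let a woman stop vaccination early and remain in follow-up. If she stops after dose 1, Month 3 is 28 + 28 + 28 = 84 days after her last dose (63 to 105). Counting from the last dose she received avoids that imbalance.

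**The case against.** The best defence is that nothing here contradicts anything else. The contraception rule, the dose-stopping rule in 6.13 and the pregnancy tests all follow the vaccination course, so the period is a consistent choice. Women planning pregnancy are excluded, and any pregnancy during the trial is followed to outcome. Amendment 1 added the contraceptive methods in response to ethics committee comments, so the topic has had outside review. The information sheet, which is not in the text reviewed, may give a longer period.

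Much of this is fair and keeps the point small. It does not remove it. Screening intent at entry does not prevent an unintended pregnancy, follow-up records harm without preventing it, and 4.12 remains the protocol's stated rule.

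Four stronger readings are tempting but unsupported:

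- **That the adverse-event windows measure fetal risk.** They are collection periods. If continued collection were the test, contraception would have to run to the end of the study.
- **That 4.12 clearly leaves the Month 2 Day 1 and Day 2 antimalarial doses uncovered.** Read literally it might, but the M0 to M2 period in 6.13 can be read to include those days.
- **That 4.12 should also declare antimalarial safety in pregnancy unknown.** The protocol makes no such statement about these drugs.
- **That this is a statistical flaw or biases an endpoint.** Nothing in the document shows either.

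**Conclusion.** The point holds as a minor participant-safety gap. Section 4.12 asks for 0 days of contraception after the last dose, immediately after calling vaccine safety in pregnancy unknown, and no other section lengthens it. What remains exposed after the entry exclusion is unintended pregnancy or a change of plan.

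The conclusion rests on the protocol text alone. The investigator's brochure and the information sheet were not available, and the protocol gives no risk-based interval. Confidence that some post-dose interval should be stated is reasonable. Confidence in 29 days as the right length is limited: it matches the protocol's own follow-up after each participant's last dose and has no further basis. The sponsor could make the change; the trial's analyses do not depend on it.

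**What to change.** In 4.12, replace the phrase that ties contraception to the time of receiving vaccinations with: *from enrolment until at least 29 days after the last vaccine dose received*. If the investigator's brochure gives an interval, use that instead. Make the same change in the information sheet if it uses the same period. It should be clear that the last dose means the final dose of the woman's course, so that Group 7, dosed at Months 0 and 2 only, stays covered between doses.

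The cost is a wording amendment and a contraception request about 29 days longer per woman, with no added visits, tests or participants. The benefit to samples is partial: the change lowers the chance of losing a blood draw to a conception in those 29 days, but a later conception could still cost the Month 6 sample.

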4.13 Source Data

Source documents are original documents, data, and records from which participants' CRF data are obtained. These include, but are not limited to, hospital records (from which medical history and previous and concurrent medication may be summarized into the CRF), clinical and office charts, registration logbook, laboratory and pharmacy records, diaries, radiographs, referral notes and correspondence.

All documents will be stored safely in confidential conditions. On all study-specific documents, other than the signed consent, the participant will be referred to by the study participant number/code, not by name.

5 TREATMENT OF TRIAL PARTICIPANTS

5.1 Description and administration of the study agents

5.1.1 Vaccines

The candidate RTS,S/AS01 vaccine to be used has been developed and manufactured by GSK Vaccines. The Quality Control Standards and Requirements for each candidate vaccine are described in separate Quality Assurance documents (e.g. release protocols, certificate of analysis) and the required approvals have been obtained. The vaccines are labelled and packed according to applicable regulatory requirements.

RTS,S/AS01E

RTS,S/AS01E is the standard formulation of the vaccine. The RTS,S antigen is presented as a lyophilized pellet with sucrose as cryoprotectant, which is reconstituted in the liquid adjuvant, AS01E. Once prepared, a standard dose of RTS,S/AS01E contains approximately 25µg of RTS,S antigen, in 0.5mL of liquid adjuvant containing 25µg MPL and 25µg QS-21. In this

study, the commercial presentation of RTS,S/AS01E will be used, i.e. a two-doses glass vial of lyophilized RTS,S antigen (50µg) to be reconstituted with a two-doses glass vial of AS01E Adjuvant System (1.0 ml). The final product for administration will be prepared by reconstitution of the lyophilized antigen with the liquid adjuvant. From the reconstituted vaccine vial:

- 0.5 ml will be withdrawn to administer RTS,S/AS01E standard doses, or
- 0.1 ml will be withdrawn to administered RTS,S/AS01E fractional doses (1/5th dose), or
- 1.0 ml will be withdrawn to administer RTS,S/AS01E double doses, or
- 0.2 ml will be withdrawn to administered double dose of RTS,S/AS01E fractional doses (1/5th dose).

All vials of vaccine provided in this study are intended for single use only.

RTS,S/AS01B (0.5 mL dose)

RTS,S/AS01B is the adult formulation of the vaccine. The RTS,S antigen is presented as a lyophilized pellet with sucrose as cryoprotectant, which is reconstituted in the liquid adjuvant, AS01B. Once prepared, a standard dose of RTS,S/AS01B contains approximately 50µg of RTS,S antigen, in 0.5mL of liquid adjuvant containing 50µg MPL and 50µg QS-21. In this study, the clinical presentation of RTS,S/AS01B will be used, i.e. a monodose glass vial of lyophilized RTS,S antigen (50µg) to be reconstituted with a mono-dose glass vial of AS01B Adjuvant System (0.5 ml). The final product for administration will be prepared by reconstitution of the lyophilized antigen with the liquid adjuvant. From the reconstituted vaccine vial:

- 0.5 ml will be withdrawn to administer RTS,S/AS01B standard doses, or
- 0.1 ml will be withdrawn to administered RTS,S/AS01B fractional doses (1/5th dose).

All vials of vaccine provided in this study are intended for single use only.

Administration of RTS,S/AS01

The procedure for administration is as follows. Disinfect the top of vaccine vial and adjuvant vial with alcohol swabs and let dry. Withdraw the contents of the adjuvant vial in a syringe and inject adjuvant into the vial of lyophilized antigen. The pellet is then dissolved by gently shaking the vial. Wait for 1 minute to ensure complete dissolution of vial contents before withdrawing the correct volume (see above). The reconstituted vaccine should be administered by slow IM injection, using a fresh 25G needle with length of 1 inch (25 mm), preferably into the non-dominant arm. Vaccine should be injected within 4 hours of reconstitution (storage at +2°C to +8°C). The study participants will be observed closely for at least 30 minutes following the administration of study vaccine, with appropriate medical treatment readily available in case of an anaphylactic reaction.

